### 10.3 Prior and Concomitant Medications

Prior and concomitant medication verbatim terms in the eCRFs will be mapped to anatomical/therapeutic/chemical class and preferred names using the WHODrug Global B3 (version 01MAR2019).

• Prior medications are defined as medications with a stop date before the date of the first dose of study drug.

Concomitant medication are medications with a start date on or after the date of first dose of study drug administration or are medications started before study drug administration and ended after study drug administration.

Prior and concomitant medications will be summarized by WHO ATC class and preferred name. These summaries will present the number and percentage of subjects using each medication. Subjects may have more than 1 medication per ATC class and preferred name. At each level of subject summarization, a subject is counted once if he/she reported 1 or more medications at that level. Each summary will be ordered by descending order of incidence of ATC class and preferred name within each ATC class.

### **10.4** Adverse Events

Treatment-emergent AEs (TEAEs) are defined as those AEs that occurred on or after the date of first dosing and those existing AEs that worsened during the study. Verbatim terms in the eCRFs will be mapped to preferred terms and system organ classes using the Medical Dictionary for Regulatory Activities (MedDRA) (version 22.0).

For this study, AEs of particular clinical importance will be reported as AESIs in the eCRFS to include: Contact dermatitis, Folliculitis and Headache which could be found from eCRF pages AESI Contact Dermatitis, AESI Folliculitis and AESI Headache, respectively. These AEs will not be summarized separately but rather will be included in the summaries described below.

Each AE summary will be summarized by system organ class and preferred term and ordered by descending order of incidence of system organ class and preferred term within each system organ class. Summaries will include the following:

- Overall summary of AEs that contain an overview of each item below.
- Subject incidence of TEAEs and total number of unique TEAEs by MedDRA system organ class and preferred term.
- Subject incidence of TEAEs by MedDRA system organ class, preferred term, and highest severity. At each level of subject summarization, a subject is classified according to the highest severity if the subject reported 1 or more events. Adverse events with missing severity will be considered severe for this summary.
- Subject incidence of TEAEs by MedDRA system organ class, preferred term, and closest relationship to study drug (Related/Not Related). At each level of subject summarization, a subject is classified according to the closest relationship if the subject reported 1 or more events. Adverse events with a missing relationship will be considered related for this summary.
- Subject incidence of serious TEAEs by MedDRA system organ class and preferred term.
- Subject incidence of TEAEs leading to discontinuation of study drug by MedDRA system organ class and preferred term.

AEs, SAEs, AESIs and AEs of action taken with study treatment as drug discontinued will be presented in data listings.

### 10.5 Clinical Laboratory Evaluation

Laboratory assessments (chemistry, hematology and urinalysis) and serologic biomarker tryptase assessment will be summarized using descriptive statistics at Baseline and at each post-baseline time point of collection (see Table 1 Schedule of Events in the protocol). Change from Baseline will also be summarized.

Shift tables for laboratory assessments with low-normal-high at baseline versus low-normal-high at follow-up for the continuous laboratory assessments will be summarized to include low to low, low to normal, low to high, normal to low, normal to normal, normal to high, high to low, high to normal, and high to high at Day 29 and at follow-up (7-10 days after Day 29 or ET).

In addition, laboratory and assessments will be listed by subject.

### 10.6 Vital Signs

Vital signs will be summarized using descriptive statistics at Baseline and at follow-up including change from Baseline. Additionally, shifts in vital sign assessments will be summarized to include the shift categories identified under laboratory assessments (Section 11.5) as well as abnormal change from Baseline and markedly abnormal change from Baseline.

Abnormal Flags will be determined as follows:

- Systolic Blood Pressure: Low= <90 mmHg; Normal= 90-140 mmHg; High= >140 mmHg;
- Diastolic Blood Pressure: Low= <50 mmHg; Normal= 50-90 mmHg; High= >90 mmHg;
- Heart Rate: Low=<50 bpm; Normal=50-100 bpm; High=>100 bpm;

Abnormal change from baseline will be determined as follows:

- Systolic Blood Pressure >=20 mmHg
- Diastolic Blood Pressure >=10 mmHg
- Heart Rate >=10 bpm

Markedly abnormal change from baseline will be determined as follows:

- Systolic Blood Pressure >=40 mmHg
- Diastolic Blood Pressure >=20 mmHg
- Heart Rate >=30 bpm

A listing of vital signs will also be presented.

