 - elimination half-life $(t_{1/2})$

- Analysis of change from Baseline in QTcF (Δ QTcF) at each post-treatment time point on the sampling day with the higher C_{max} (Day 1 or Day 29)
- Concentration-QTc analysis investigating the relationship between tapinar of plasma concentration and ΔQTcF, if data permit
- Mean change from Baseline to Day 29 in PGA, PASI, and %BSA

Statistical Methods:

Safety and PK data will be presented in tabular and/or graphical format and summarized descriptively.

For cardiodynamic ECG assessments, the primary analysis will be based on by-time point analysis to evaluate the effect of tapinarof cream, 1% on the $\Delta QTcF$ at each post-dosing time point using the Intersection Union Test. The effect of tapinarof on ΔHR , ΔPR , and ΔQRS will also be evaluated using the Intersection Union Test. An analysis of categorical outliers will also be performed for changes in HR, PR, QRS, QTcF, T-wave morphology and U-wave presence. In addition, a potential concentration-QTc analysis will be performed if a sufficient number of PK samples are measurable, i.e., above the lower limit of quantification, to provide a PK profile in most subjects. In this concentration-QTc analysis, the relationship between tapinarof plasma concentrations and $\Delta QTcF$ will be evaluated using a linear mixed-effects modeling approach.

PGA, PASI, and %BSA will be compared to Baseline values using a one sample t-test.

SCHEDULE OF ASSESSMENTS

Table 1: Schedule of Assessments

		Treatment Period (Tapinarof Cream, 1% Once Daily)						Follow-up		
Procedure	Screening (up to 34 days prior to Day 1)	Day -1	Baseline Day 1	Day 2	Day 8	Day 15	Day 22	Day 29	Day 30	(7-10 days after Day 29) or ET
	Visit 1	Visit 2	Visit 3	Visit 4	Phone Call	Visit 5	Phone Call	Visit 6	Visit 7	Visit 8
Informed consent	X									
Inclusion and exclusion criteria	X	X	X							
Demography	X									
Brief physical exam (including height, weight and BMI at Screening)	X									X
Medical history (including year of psoriasis diagnosis)	X									
Pregnancy test (WOCBP)	X		X							X
PGA, PASI, and % BSA evaluation ^a	X		X					X		
HIV, Hep B and Hep C Screen	X									
Laboratory assessments (chemistry including liver chemistries, hematology, urinalysis)	X		X					X		X
LTS assessment by Investigator			X			X		X		
Single 12-lead ECG	X									X
Continuous Holter Monitoring		X ^b	X ^c	X ^d				X ^c	X ^d	
Vital signs (pre-dose; HR, BP, and temperature)	X		X							X
Randomization			X							

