Study drug Dispensation / Collection			X			X		X		
Training on drug application			X	X	X	X	X			
Dispense/collect subject diary			X			X		X		
Tapinarof cream administration in- clinic under site supervision			X	X		X		X		
Serial PK profile samples ^e			X	X		X		X	X	
			X	X				X	X	
AE/SAE review	X	X	X	X	X	X	X	X	X	X
Concomitant medication review	X	X	X	X	X	X	X	X	X	X

Note: Phone calls to subjects are on Day 8 and Day 22

Abbreviations: %BSA = percent body surface area; AE = adverse event; BMI = body mass index; BP = blood pressure; ECG = electrocardiogram; ET = early termination; Hep = hepatitis; HIV = human immunodeficiency virus; LTS = local tolerability scale; PGA = Physician Global Assessment; PASI = Psoriasis Area and Severity Index; PK = pharmacokinetic; SAE = serious adverse event; WOCBP = women of childbearing potential

- ^a The subject's scalp, palms, and soles should be excluded from the %BSA calculations.
- b On Day -1, a Holter monitor will be attached for approximately 13 hours to collect pre-treatment, time-matched ECG data. 12-lead ECGs will be extracted from the continuous recording at time points corresponding to time points on Day 1 and Day 29. Subjects will rest in a supine or semi-recumbent position for at least 10 minutes before and 5 minutes after each time point for ECG extraction.
- ^c On Day 1 and Day 29, a Holter monitor will be attached one hour prior to dosing and for 12 hours post-dose. 12-lead ECGs will be extracted at the same time points as PK samples, i.e., pre-dose and at 1, 2, 3, 4, 5, 8, and 12 hours post-dose. Subjects will rest in a supine or semi-recumbent position for at least 10 minutes before and 5 minutes after each time point for ECG extraction. All ECG extractions will be performed immediately before the PK sample is drawn.
- d On Day 2 and Day 30, a Holter monitor will be attached for one hour prior to the 24-hour post-dose PK time point to allow for extraction of 12-lead ECGs corresponding to the 24-hour post-dose PK time point. Subjects will rest in a supine or semi-recumbent position for at least 10 minutes before and 5 minutes after the time point for ECG extraction. The ECG extraction will be performed immediately before the PK sample is drawn.

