1.2. Rationale for Study Design and Dose

This study includes a 29-day, open-label treatment phase in which subjects will receive tapinar of cream, 1% once daily for 29 days. Tapinarof cream has been investigated in prior studies at concentrations from 0.5% to 8.0% and at once and twice daily dosing frequencies. The 1% concentration applied once daily was chosen as the dose and dosing frequency to take forward in the clinical development program based on the data from the GSK Phase 2b clinical study in subjects with psoriasis (Study 203120). In that study, applications of tapinarof at concentrations of 0.5% and 1% applied once or twice daily were evaluated. Overall, both concentrations demonstrated an acceptable safety profile when applied once or twice daily. A once daily application regimen may reduce systemic exposure as the skin heals, thereby providing a better safety profile for a drug intended for long-term use to treat a chronic condition. Based on the efficacy and safety data from Study 203120, a regimen of 1% once daily was chosen as the tapinar of concentration and dosing frequency to be investigated in this study and intended for registration. Tapinarof has a unique PK profile whereby the highest plasma concentrations are observed in the first week of the treatment period followed by a subsequent decline to undetectable or near undetectable levels after multiple weeks of dosing. Accumulation of drug after multiple dosing has not been observed in any clinical study with tapinar of to date. The 29-day treatment phase was selected to ensure steady-state is achieved and to provide a treatment duration that allows for evaluation of safety in this population with extensive disease that has not been evaluated to date.

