In a nonclinical study in minipigs using IV administration, reversible decreases in arterial blood pressure and PR interval were observed; however, in this study and repeat dermal toxicity studies, there were no effects on QT interval or HR. Repeat-dose dermal toxicity studies also showed findings related to the liver (increased weights and hepatocellular hypertrophy/regeneration) and thymus (thymic cortex depletion in adult rabbits and rats; changes in thymus weight, microscopic decreased cellularity, and changes in thymic T cell maturation in juvenile rats) with associated secondary hematological findings. Thymic findings were also noted in repeat adult and juvenile rat studies; however, there were no clinically relevant AEs/serious adverse events (SAEs) reported.

To mitigate potential systemic risks, subjects will be monitored for AEs and any abnormal vital signs, physical examination, and laboratory test results.

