6.3.3. Vital Signs

Vital signs will be measured before blood collection for clinical laboratory assessments and PK analysis (where applicable) and will include measurement of systolic and diastolic BP, HR, and body temperature. Subjects should be in a supine or semi-recumbent position for at least 5 minutes before vital signs measurement.

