7.10. Visit 8; Follow-Up (7-10 days After Day 29)/Early Termination

Follow-up/Early Termination assessments are as follows:

- ECG recording
- Urine pregnancy test (WOCBP only)
- Brief physical examination
- Vital signs measurements
- Blood and urine sample collection for clinical laboratory tests
- AE recording
- Concomitant medication recording

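### No blood pressure is scheduled on treatment for completers, although vital signs are a primary safety endpoint, and the SAP 10.6 change flags as written count only rises

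*SAP*

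**What the plan says.** Protocol Section 2 lists five endpoints under the primary safety objective: adverse events, laboratory and biomarker values, vital signs, ECGs, and local tolerability scores.

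The Table 1 row "Vital signs (pre-dose; HR, BP, and temperature" is marked at Screening, Day 1 and Follow-up/ET only. The visit lists in Section 7 agree: vital signs appear in 7.1, 7.3 and 7.10 ("Visit 8; Follow-Up (7-10 days After Day 29)/Early Termination") and in no list for Days 2, 15, 29 or 30. SAP 10.6 follows the same schedule: "Vital signs will be summarized using descriptive statistics at Baseline and at follow-up including change from Baseline".

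Two protocol sections bear on why timing matters. Section 1.2 says that "the highest plasma concentrations are observed in the first week of the treatment period", with a later decline to levels at or near the limit of detection. Section 1.3.1.2 reports from an intravenous minipig study that "reversible decreases in arterial blood pressure and PR interval were observed", and then says: "To mitigate potential systemic risks, subjects will be monitored for AEs and any abnormal vital signs, physical examination, and laboratory test results".

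For change from baseline, SAP 10.6 sets abnormal limits of >=20 mmHg systolic, >=10 mmHg diastolic and >=10 bpm heart rate, and markedly abnormal limits of >=40, >=20 and >=30. None has a sign or a direction. SAP Section 6 defines change as the post-baseline value minus the baseline value.

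**The concern.** The study is meant to describe safety under maximal use. For a completer, the blood pressure endpoint compares a value before any drug with a value taken at least a week after the last application. It can say little about blood pressure while the drug is being absorbed. The protocol names vital-sign monitoring as a mitigation for systemic risk, but for blood pressure the schedule does not provide it during treatment. Clinically significant vital-sign changes are to be reported as adverse events, but a change that is not measured may never be reported.

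The second point concerns the analysis of what is collected. The only blood pressure effect the protocol describes is a decrease, and a decrease is what the change flags miss when the thresholds are combined with the signed formula. Appendix D, Table 2 of the SAP writes out both an increase and a decrease rule for heart rate; SAP 10.6 does not.

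**Working it through.** The plan states no figure to reproduce on this point. The sample size of about 20 is set by feasibility and is not affected.

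**Step 1: on-treatment coverage of the primary safety endpoints (Table 1, Section 7).**

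| Endpoint | Scheduled on treatment |
|---|---|
| Adverse events | Every visit and phone call |
| Laboratory values | Day 29 |
| ECG | Holter on Days 1 and 29, with 24-hour points on Days 2 and 30 |
| Local tolerability | Days 15 and 29 |
| Vital signs: heart rate | From the Holter only |
| Vital signs: blood pressure, temperature | None after the first application |

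**Step 2: length of the gap.** Follow-up falls on Day 29 + 7 = 36 to Day 29 + 10 = 39. Measured from the Day 1 pre-dose reading, the gap is 36 - 1 = 35 to 39 - 1 = 38 days. Four clinic visits lie inside it (Days 2, 15, 29, 30), with no scheduled blood pressure at any of them and none after dosing on Day 1.

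**Step 3: the signed rule on examples.** Change = post-baseline minus baseline; systolic Low is <90 mmHg.

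| Systolic | Change | >=20 met | >=40 met | Low flag |
|---|---|---|---|---|
| 100 to 120 | +20 | yes | no | no |
| 130 to 110 | -20 | no | no | no |
| 130 to 90 | -40 | no | no | no |
| 140 to 95 | -45 | no | no | no |

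**Step 4: largest fall from a normal baseline that raises no flag.** Start at the upper normal limit in SAP 10.6 and end at the lower one, which still counts as Normal.
- Systolic: 90 - 140 = -50 mmHg (markedly abnormal size: 40)
- Diastolic: 50 - 90 = -40 mmHg (markedly abnormal size: 20)
- Heart rate: 50 - 100 = -50 bpm (markedly abnormal size: 30)

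Each exceeds the plan's own threshold for a marked change.

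**Step 5: expected number of 20 subjects flagged for a systolic change of at least 20 mmHg.** The documents give no mean or SD for the change, so both are assumed here, with a normal distribution. Rises only: 20 × P(change >= 20). Both directions: add 20 × P(change <= -20).

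| Assumed SD | Mean 0: rises only / both | Mean -10: rises only / both |
|---|---|---|
| 10 | 0.46 / 0.91 | 0.03 / 3.20 |
| 12 | 0.96 / 1.91 | 0.12 / 4.17 |
| 15 | 1.82 / 3.65 | 0.46 / 5.50 |

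With no mean shift, the rises-only rule flags half the large changes. With a mean fall of 10 mmHg it flags fewer than one subject in 20, where a rule in both directions would flag three to six.

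**Step 6: room in the existing schedule.** Post-dose ECG points are at hours 1, 2, 3, 4, 5, 8 and 12 on Days 1 and 29 (7 + 7) plus the 24-hour points on Days 2 and 30 (1 + 1), giving 16. At these, "Subjects will rest in a supine or semi-recumbent position for at least 10 minutes before and 5 minutes after each time point". Section 6.3.3 asks for less: "Subjects should be in a supine or semi-recumbent position for at least 5 minutes before vital signs measurement". Section 6.3.7 typically places the ECG window in the last 5 minutes of a 15-minute rest. That leaves 15 - 5 = 10 minutes beforehand: 5 for the required rest and 5 for the reading.

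**The case against.** The protocol and SAP agree with each other on the schedule, so this is a design choice and not a contradiction. Nothing in the documents promises blood pressure during treatment. Clinically significant vital-sign changes are adverse events, and adverse events are reviewed at every contact. The minipig finding followed intravenous dosing and was reversible, and the protocol reports no blood pressure finding in the dermal studies. Ten clinical studies were completed, with details left to the investigator's brochure, which may have justified sparse monitoring and cannot be judged here. All of this stands, and it is why the first part is a recommended improvement and not an error. It does not give the study any planned blood pressure under exposure.

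Section 6.3.3 places vital signs ahead of laboratory and PK draws, which might be read as requiring them on Day 29. The text says where applicable and adds no visit.

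On direction, a bare magnitude could be read as absolute change, and the unflagged falls in Step 4 are extreme cases. That reading is possible, but it shows that the text is open to two interpretations. Falls are also not hidden altogether: they enter the mean and minimum of the change summary, the listing, and the Low shift if they cross the limit. With no on-treatment reading, the flags affect only one off-drug comparison per completer, and on-treatment heart rate is analysed separately in Appendix D.

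Finally, Day 29 may itself be a day of low exposure on the protocol's own account. That makes the Day 1 post-dose reading the more important of the two. Day 29 is still worth having as the last dosing day.

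**Conclusion.** Both parts hold. For subjects who complete treatment, blood pressure and temperature have no scheduled value for 35-38 days, covering everything after the first application up to follow-up. Vital signs are the only primary safety endpoint with no scheduled on-treatment value apart from heart rate. An early-termination visit or an unscheduled reading could supply one, but SAP Section 6 lists unscheduled visits without summarising them.

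The SAP 10.6 change thresholds, combined with the SAP Section 6 formula, flag only rises. Falls of up to 50 mmHg systolic, 40 mmHg diastolic and 50 bpm from a normal baseline can pass without any abnormal, marked or Low flag. This rests on reading the formula literally; if absolute change was intended, the text needs to say so.

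This should be fixed. No sample size or formal test is affected. PR interval is outside this point, because its change is analysed on treatment by time point.

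**What to change.** **SAP 10.6 (wording only).** Apply the existing blood pressure and heart rate thresholds to change in either direction, and tabulate increases and decreases separately. Correct the cross-reference to Section 11.5 for the laboratory shift categories, which are in SAP 10.5.

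**Protocol, if enrolment is open.** Add vital signs to Table 1 and Section 7 at visits already held: at least one post-dose reading during the Day 1 PK stay, one on Day 29, and optionally one on Day 15. On Holter days, take the reading during the existing rest, before the ECG window and the PK draw. Adjust the Section 7 note that assessments are done before dosing, reconcile the opening sentence of Section 6.3.3 with Table 1, and have SAP 10.6 summarise by visit. The cost is a short amendment, added eCRF fields, by-visit text in the SAP and a few minutes per reading.

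**If enrolment has closed.** The documents do not give enrolment status; the SAP is dated February 2020 and the protocol April 2019. In that case, state in the study report that no blood pressure was scheduled on treatment and that for completers the endpoint describes off-drug values.

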### **10.7 Local Tolerability Scale**

Local tolerability scale (LTS) overall score for dryness, erythema, and peeling will be summarized using descriptive statistics at Baseline and at Days 15 and 29 as will the number and percent of subjects who apply study drug to the following sensitive areas: face, neck, skin folds, axilla, inframammary, anal crux, and genitalia. If 5 more subjects treat a sensitive area(s) at any time during the treatment period, LTS scores will be summarized at Baseline and Days 15 and 29 for that specific area(s).

In addition, LTS scores will be listed by subject overall and by sensitive area as applicable.

### 10.8 Physical Examination

Nicotine usage assessed at Baseline and pregnancy test results at Screening, Baseline, and Follow-up will be presented in listings.

### 10.9 Cardiodynamic Assessments (Continuous Holter Monitoring)

ECG data from Baseline and while on study treatment will be collected using a 12-lead Holter monitor. ECG data will be summarized in tables, presented graphically in figures and listed in data listings by The final -signed SAP including mock TFLs can be found in Appendix D.

### 11. PHARMACOKINETIC ANALYSES

Unless otherwise specified below, missing sampling or concentration values should not be imputed, but left missing in the calculation of derived PK parameters. If the actual sampling time is missing, but a valid concentration value has been measured, the scheduled protocol time will be used for the calculation of derived PK parameters. A missing pre-dose value will be set to 0 for the PK calculations corresponding to an observation at dosing time.

All pharmacokinetic (PK) analyses and generation of the tables, figures, and listings (TFLs) will be performed using a validated installation of Phoenix WinNonlin® version 8.1 ( ) as part of a 21 CFR Part 11 compliant database system (Pharsight Knowledge Database "PKS").

Blood samples for the analysis of tapinarof and its metabolite, tapinarof sulfate, will be collected pre-dose and post dose on Day 1 and Day 2 (Visits 3 and 4) as well as Day 29 and Day 30 (Visits 6 and 7) at 1, 2, 3, 4, 5, 8, 12, and 24 hours after dosing. On Day 15 (Visit 5), samples will be collected pre-dose and at 2- and 4-hours post dose ( $\pm 10$  mins). Samples collected outside the pre-determined intervals will be flagged and footnoted.

PK data from the PK population will be presented in listings. Plasma concentrations will be summarized using descriptive statistics. The number of plasma samples that were BQL will be summarized by subject and overall.

PK parameter estimates for tapinarof and its metabolite tapinarof sulfate on Day 1 and Day 29 will be calculated using non-compartmental analysis (NCA) of the plasma concentration versus time data utilizing actual sample collection time. NCA will be conducted using validated PK data analysis software (Phoenix WinNonlin version 8.1). AUC values will be estimated using the linear up-log down method. A minimum number of 3 data points are required for determination of AUC. The apparent first-order terminal elimination rate constant ( $\lambda_z$ ) will be calculated as the negative of the slope from linear regression of the semi-log concentration-time curve during the terminal phase. The apparent first-order terminal elimination half-life,  $t_{1/2}$ , will be calculated as  $0.693/\lambda_z$ . A minimum of three descending concentration-time points, excluding the Cmax, above the lower limit of quantification (LLOQ) will be used in the estimation of the terminal phase rate constant ( $\lambda_z$ ), for the determination of the terminal half-life ( $t_{1/2}$ ). PK parameter estimates are listed in Table 1, other parameters can be added, if data permits.

PK parameters Cmax and  $AUC_{0-\tau}$  will also be normalized to %BSA treated by dividing each parameter by cm^2 of body surface area of disease. For this calculation, 1% BSA is equal to 185 cm^2.

Imputation of BQL data should be addressed as follows:

- If a BQL value occurs in a profile before the first measurable concentration, it will be assigned a value of zero concentration. Therefore, a subject with BQL values for the entire dosing interval will have a Cmax of zero.
- If a BQL value occurs after a measurable concentration in a profile and is followed by a value above the lower limit of quantitation (LLOQ), then BQL should be treated as 'missing'.
- If a BQL value occurs at the end of the collection interval (after the last quantifiable concentration) it will generally be treated as 'missing'
- If two BQL values occur in succession after Cmax, the profile will be deemed to have terminated at the first BLQ value and any subsequent concentrations will be omitted from pharmacokinetic calculations and individual plots, which are to reflect data that were used in the NCA, but will be maintained in concentration-time tables and plots of mean data

BQL values will be treated as zero for summary statistics tables or mean figures.

On a case by case basis, it may be necessary to exclude individual PK concentration values for the calculation of derived PK parameters because they are erroneous, abnormal or appear

Dermavant Sciences GmbH DMVT-505-2002

Statistical Analysis Plan 06-FEB-2020

implausible to the pharmacokineticist in charge of the analysis. Any excluded data will be flagged in the individual data listings. The reason for exclusion will also be documented. If the exclusion has a meaningful impact on the overall interpretation of the results, then it will be discussed.

Dermavant Sciences GmbH

